The aim of this observational study was to assess whether increases in the proinflammatory cytokine IL-6 would increase pre- to post-influenza vaccine, and whether these changes would correlate with changes in performance on reward tasks assessing motivation (monetary reward), learning (monetary reward) and sensitivity (monetary and general social reward). *Methods*: 41 healthy UCLA undergraduate students participated in this pre-post within-subjects study. Participants completed baseline assessment of reward tasks, a week of daily diary assessment, and were then scheduled to receive the annual influenza vaccine. Participants provided blood samples prior and 24-29 hours after the vaccine. Participants completed behavioral reward tasks 24-29 hours after the vaccine; this 24-29 hour period was based on prior research showing an IL-6 peak one day post-influenza vaccine. **Results**: Levels of IL-6 increased significantly from pre-to post-vaccine, but performance on the reward tasks did not significantly differ from pre- to post-vaccine. However, as hypothesized, increases in IL-6 were correlated with decreases in reward motivation for monetary reward, and decreases in attentional bias to positive faces (an index of sensitivity to general social reward). Changes in sensitivity to monetary reward, as operationalized through parameters in the reward motivation task, were not associated with changes in IL-6. Increases in IL-6 correlated with increases in reward responsiveness on a standardized learning task, although sample size for computational analyses was not sufficient to identify whether this was driven by increases in learning or sensitivity. **Conclusion**: Consistent with hypotheses, mild increases in IL-6 following influenza vaccination correlated with decreases in motivation for monetary reward, and decreases in sensitivity to general social stimuli. Contrary to hypotheses, increases in IL-6 were not correlated with change in sensitivity for monetary reward and were associated with increases in reward responsiveness on a reward learning task. These data suggest an association between the proinflammatory cytokine IL-6 and performance on reward tasks in multiple reward dimensions for both non-social and general social reward.

[figure not shown]

Figure 2. Changes in depressive symptoms over 2 years after endotoxin protocol (vs. placebo)

[figure not shown]

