In our endotoxin study of younger adults, the effect of endotoxin on depressed mood was large in females ($d=0.70$) while minimal in males ($d=0.003$).¹⁴ Among older adults, we expect to see a smaller but still substantial difference of effect between sexes. In our endotoxin study of older females (K23AG049085, PI [name]), as shown in C.1.1.3, the effect size of endotoxin on depressed mood was still large but expectedly smaller ($d=0.51$) than in younger females. For Aim 1, based on these estimates, the assumed minimal effect size in older males ($d=0.003$), and the use of matching and multivariate regression analyses, with 40 older healthy females and 40 older healthy males, we expect a power $>80\%$ ($\alpha=.05$, two-tailed). For Aim 2, assessing differences between younger and older females, our previous work with several of the behavioral reward tasks has yielded moderate effect sizes when assessing the relationship between increases in IL-6 and task performance (e.g., $f^2 = 0.22, 0.32$). Given this range of effect sizes, a multiple regression analysis with three predictors of interest (age, group, age x group interaction) and two covariates (BMI, education level) would require a sample size of 38 to 75 to detect effects with 0.80 power. This work has relied on very mild increases in IL-6, and we expect endotoxin to yield stronger effects. Indeed, prior work with the endotoxin model has shown significant differences on a reward motivation task with a sample of 29 participants (15 saline placebo, 14 endotoxin),⁹² and greater feelings of social disconnection following endotoxin vs. placebo were observed in a small sample of women ($n=20$; age 18-36) in our previous study. Thus, the current study aims to recruit 40 premenopausal women with equal randomization between the endotoxin and saline group, and an additional 40 females will be drawn from the parent study for a total sample of 80.

C.3. Interpretation of Results and Potential Concerns

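### Aim 2 is sized on effects that are not age-by-condition interactions, so the implied 80% power of 80 women for the Aim 2 question is unsupported

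*Combined protocol and SAP*

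**What the plan says.** The second hypothesis in the Specific Aims is that younger women respond more strongly to endotoxin than older women. C.2.8 analyses Aim 2 as it does Aim 1, with age group replacing sex: a two-by-two layout of group by condition in a linear mixed model. C.2.2 puts 20 younger women on endotoxin and 20 on placebo. The 40 older women come from a 40:40 randomisation stratified by sex, so about 20 per condition.

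C.2.9 supports the Aim 2 sample size in three steps.

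- It says that previous work with several reward tasks "has yielded moderate effect sizes when assessing the relationship between increases in IL-6 and task performance", and gives f² values of 0.22 and 0.32 as examples.
- It states that a multiple regression with three predictors of interest (age, group and their product) and two covariates (BMI and education) "would require a sample size of 38 to 75 to detect effects with 0.80 power".
- It notes that the earlier work involved very mild IL-6 increases, expects endotoxin to act more strongly, and cites two endotoxin-versus-placebo comparisons with 29 and 20 participants. It then settles on 80 women.

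The same section quotes d=0.70 for the endotoxin effect on depressed mood in younger females and d=0.51 in older females. It uses these figures for Aim 1 and not for Aim 2.

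**The concern.** The quantity used for sizing is not the quantity Aim 2 tests. An association between IL-6 change and task performance within one sample says nothing about how far the endotoxin effect differs between two age groups. The two supporting studies compare endotoxin with placebo and contain no age contrast. The expectation that endotoxin will act more strongly than a mild stimulus concerns the size of the endotoxin effect, not its difference by age.

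C.2.9 does not name the source of the f² values. The description fits the influenza-vaccine study in C.1.3, but that link is an inference. If it is right, the source has neither a placebo arm nor age groups: "41 healthy UCLA undergraduate students participated in this pre-post within-subjects study". IL-6 rose in that study, "but performance on the reward tasks did not significantly differ from pre- to post-vaccine".

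A reader who sees 80 set against a requirement of 38 to 75 will conclude that Aim 2 has at least 80% power. A non-significant age comparison could then be taken as evidence that sensitivity to inflammation does not change with age, which is the question behind the aging-paradox rationale in the Specific Aims.

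**Working it through.** **Inputs.** From C.2.9: f² = 0.22 and 0.32; three tested predictors of five; power 0.80; d = 0.70 (younger) and 0.51 (older). From C.2.2: 20 per cell, N = 80. Two-sided alpha 0.05 is stated for Aim 1 and assumed here for Aim 2.

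**1. The plan's own range.** I used the noncentral F test for an increase in R², with λ = f²·N and error df = N − 6. Required N for 80% power:

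| Predictors tested (of 5) | f² = 0.32 | f² = 0.22 |
|---|---|---|
| 3, as the plan describes | 39 | 54 |
| 1 (interaction only) | 27 | 38 |
| 5 | 46 | 65 |

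With three tested predictors the lower figure of 38 is reproduced to within one participant. The upper figure of 75 is not: it needs f² of about 0.154. None of the variants tried (other numbers of predictors, alphas and power levels, or the values read as f or R²) gave the pair 38 and 75. The discrepancy is conservative. At N = 80 the joint three-predictor test has power 94% at f² = 0.22 and 99% at f² = 0.32.

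**2. What those f² values would mean as an interaction.** Let D be the endotoxin effect in younger women minus that in older women, in within-cell SD units. In a balanced two-by-two layout the interaction explains variance (D/4)², so f² = (D/4)² and D = 4√f².

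- f² = 0.22: D = 4 × 0.469 = 1.88 SD.
- f² = 0.32: D = 4 × 0.566 = 2.26 SD.

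Both are more than twice the whole endotoxin effect quoted for younger women (0.70).

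**3. What 20 per cell can detect.** SE(D) = √(4/20) = 0.447 SD, with 4 × 20 − 4 = 76 df. By the noncentral t distribution, 80% power is reached at D of about 1.27 SD. The 95% CI half-width is about 1.99 × 0.447 = 0.89 SD. This takes a single time point, no covariate gain and no dropout.

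**4. Depressed mood, the only outcome with effect sizes by age.**

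- 0.70 against zero: D = 0.70, power about 34%.
- 0.70 against 0.51: D = 0.19, D/SE = 0.42, power about 7%. The corresponding f² is (0.19/4)² = 0.0023.

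**5. Sensitivity to baseline adjustment.** The documents give no baseline–outcome correlation ρ, so these values are assumed. The SE shrinks by √(1 − ρ²).

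| ρ | Power, D = 0.19 | Power, D = 0.70 |
|---|---|---|
| 0 | 7% | 34% |
| 0.5 | 8% | 43% |
| 0.7 | 9% | 58% |
| 0.9 | 16% | 94% |

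Only the combination of no response at all in older women and a very high correlation passes 80%.

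**6. How firm is the 0.19?** C.1.1.1 gives a mean age of 24.1 for the younger-adult study, whereas Aim 2 recruits women aged 30 to 40. C.1.1.3 reports the older-women effect size of 0.51 with P = 0.017 and N = 35, without defining the metric. If it were a between-arm d with equal arms (an assumption), t = 0.51/√(4/35) = 1.51 and P = 0.14. P = 0.017 would need d of about 0.85. The 0.51 and the 0.70 may therefore be on different scales.

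**The case against.** The strongest reply is that C.2.9 sizes Aim 2 on reward tasks, not mood, and that C.2.8 counts the two main effects as well as the interaction among its key results. A joint three-predictor test partly matches that, and on the quoted f² values 80 women are ample for it. The f² values are given as examples, so an unquoted value near 0.15 may lie behind the 75. The mixed model uses repeated measures, which could improve precision.

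Part of this stands. The range mismatch is confined to its upper end and does not make the study too small. The plan never subtracts 0.51 from 0.70, so the 7% is not a planning assumption of its own. But the joint test can be significant through an endotoxin main effect alone, which leaves the Aim 2 hypothesis unanswered.

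Three stronger readings are tempting, and the documents support none of them:

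- That Aim 2 has 7% power. The figure covers one outcome and joins two effect sizes from samples and metrics that may not be comparable.
- That the whole 38-to-75 range is wrong. The lower end reproduces.
- That a null result would be worthless. A confidence interval could still exclude very large age differences.

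**Conclusion.** The implied 80% power for the Aim 2 question is unsupported, because no effect cited for it in C.2.9 is an age-by-condition effect. At 20 per cell the design has 80% power only for a difference in endotoxin effect of about 1.27 SD, on the assumptions of step 3 and two-sided alpha 0.05. For depressed mood, power runs from about 7% (face-value figures, illustrative) to about 34% (no effect in older women) before any covariate gain. For the reward tasks the documents give no age-difference effect, so neither 80% nor any other figure can be derived. The unexplained 75 is a secondary, conservative traceability defect.

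**What to change.** In C.2.9:

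- Replace the f²-based sentence and the 38-to-75 range with the age-by-condition difference detectable at 20 per cell (about 1.27 SD at 80% power, two-sided alpha 0.05), and state the assumptions on time point, covariates and dropout.
- Give depressed-mood power as an illustrative range of about 7% to 34%, noting the age of the younger source sample and the undefined metric of the 0.51.
- Say that power for the reward tasks cannot be derived from the available data.

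In C.2.8, commit to reporting the Aim 2 interaction with its 95% CI, and state that a non-significant result will not be read as evidence of no age difference.

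The Aim 2 hypothesis and recruitment stay as they are. The cost is rewording and a less favourable power statement.

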
C.2.2. Overview of study design

To address Aim 1, examining sex differences in affective sensitivity to inflammation among older adults, we will select a total of 80 healthy older adults aged 60-80 years (40 males and 40 females), who are absent of current psychiatric illnesses, insomnia, and medical conditions (e.g., inflammatory disorders), into a placebo-controlled, randomized, double-blind, experimental inflammatory challenge protocol. Participants will be randomly assigned to receive either endotoxin (n=40) or placebo (n=40) in a between-subjects manner, stratified by sex. To address Aim 2, examining age differences in affective sensitivity to inflammation among females, we will recruit an additional 40 healthy premenopausal adult women (age 30-40) to be randomly assigned to receive endotoxin (n=20) or placebo (n=20).

For all participants, administration of endotoxin (0.8 ng/kg body weight vs. placebo), will be followed by self-report measures of depressed mood, negative and positive affect, and sickness symptoms (e.g., fatigue) assessed hourly over a 12-hour period; objective ratings of depressive symptoms by an observer blind to condition will be made every 2 hours. Behavioral tasks will be administered to coincide with peak onset of depressed mood, which we have previously shown to occur at 2 hours in both older and younger adults. Our prior protocol duration was 6 hours, but the current proposal will test for the presence of delayed termination of response^{57,58} and extend protocol duration to 12 hours. At baseline and starting two hours post-injection, at peak cytokine- and depressed mood responses, participants will complete the Probabilistic Reward Learning task⁵⁰⁻⁵², the Effort Expenditure for Reward Task,⁵⁹ the Social Choice task (i.e., intersection of reward

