motivation and sensitivity for social reward),^{60,61} the Emotional Face Recognition task,⁶² and assessment of cognitive function.⁶³ At two hours post-injection only, participants will complete the Cyberball Social Exclusion task (i.e., self-reported sensitivity to social rejection).^{11,64} Proinflammatory cytokines levels will be repeatedly assessed through hourly blood draws, and measures of activation of the inflammatory transcription factor (NF- κ B) and inflammatory gene expression, as well as assessment of dopaminergic activity, will be obtained during the first half of the protocol prior to and immediately after peak cytokine responses. A between-subject parallel design will be used for the following reasons: 1) the proposed study involves endotoxin administration, and in a hypothetical crossover design, subjects who experience aversive sickness symptoms from endotoxin (possibly also from placebo due to expectation) might drop out, which would introduce bias and invalidate the results; 2) the effect of endotoxin on inflammation might not resolve between sessions; 3) repeated exposure to behavioral tests of social exclusion might alter responses; 4) two sessions have high subject burden; 5) distinct endotoxin and placebo groups are required for the 2-year follow-up.

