Experimental task: subjective sensitivity to social rejection (Cyberball Social Exclusion Task) Socio-emotional mechanisms of depression will be examined in this study as they are particularly significant to older adults, who often experience objective and subjective social isolation, which is associated with depression risk.⁸⁶ Feelings of 'social disconnection' play a critical role in the onset and perpetuation of (non-inflammatory forms of) depression.⁸⁷ Inflammatory processes can trigger social withdrawal⁸⁸ and increase feelings of distress and related neural sensitivity (i.e., activation of the dorsal anterior cingulate cortex).⁹ Using the Cyberball Social Exclusion Task,⁶⁴ we will examine feelings of social distress. Briefly, participants will be told that they will play a virtual ball-tossing game with two other players over the Internet. In reality, they will play with a preset computer program. In the first round (inclusion), participants will play with the two other players for the entire period. In the second round (exclusion), participants will receive the ball for seven throws and then will be excluded for the rest of the round when the two players will stop throwing the ball to the participant. Following this task, they will complete a self-report measure of social distress in response to social exclusion.⁸⁹

Experimental task: negative bias to emotional face recognition (Emotion Recognition Task) Depressed subjects have a negative bias in the perception of emotions expressed in faces as they tend to interpret neutral faces as sad and happy faces as neutral.⁴⁹ Furthermore, such a bias appears to play a role in the etiology and maintenance of depression as it predicts relapse in currently depressed and remitted patients.⁴⁰ Emotional Face Recognition Task⁶² consists in showing participants a series of black and white photographs (Ekman Pictures of facial affect), in which facial expression is morphed from Neutral to either Sad, Angry, or Fearful.⁹⁰ For each image, they will be asked to make a forced choice about the emotion expressed, and rate their certainty on a 0-9 scale. Earlier recognition of a Sad face with certainty would be indicative of negative bias.

Positive Affect Responding

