All measured variables will be assessed for distributional qualities and transformed if necessary for use in the selected statistical models. Adequacy of random assignment and matching will be tested using t-tests and chi-square tests as appropriate. All pre-classification variables (age, BMI, insomnia, medical comorbidity, prior depression history) and baseline values of outcomes will be compared; those that are significantly different between females and males (at $P < 0.15$) will be considered for inclusion as covariates in the main analyses. Missing data patterns will be analyzed to assess the potential for biased parameter estimates; missing data will not be imputed as the methods selected allow for missing data under common missingness assumptions. The basic design for Aim 1 is a 2 group (females vs. males) by 2 condition (endotoxin vs. placebo) independent balanced analysis of variance (ANOVA) with one or repeated outcome measures (times: T_{hr} where $hr = 0$ for baseline, 0.5 to 12 post-infusion; peak cytokine concentration at T_2)¹², conducted with linear mixed models (LMM). The number of repeated measures varies by assessment. The key results are the main effects of sex, condition, and their interaction; for those analyses with repeated measures, the two main effects and interaction will further interact with the time variable. Other planned analyses include lagged (time series) relationships between cytokine outcomes and affect measures via general linear modeling (GLM). Standard pharmacokinetic parameters (e.g., AUC, C_{MAX} , T_{MAX}) may also be used to create summary cytokine and affect profile outcomes. Finally, covariates (i.e., pre-classification variables such as prior depression history, insomnia, or baseline CRP) will be tested if appropriate (i.e., $p < 0.15$) to assess the robustness of the results and further explicate the findings. **Aim 1** is tested with LMM for the following outcomes (timepoints): POMS Depression, DACL, Social Disconnection (T_0 , $T_1 - T_{12}$), Observer rated depression (T_0 , $T_{2,4,6,8,12}$), Cyberball Social Exclusion Task (T_2), Emotion Tasks (T_0 , T_2), Social Support Questionnaire (T_0 , T_2), Social Choice Task (T_0 , T_2), Reward Response (T_0 , T_2), Reward Learning (T_0 , T_2), and Reward Motivation (T_0 , T_2). The basic design for **Aim 2** is identical to Aim 1 but using age as the group variable (young females vs. older females) instead of sex. **Aim 3** is restricted to the endotoxin condition to examine the correlations between inflammatory responses and affective responses to endotoxin according to sex and age. These correlations will be examined using mixed-effects model linear regression, and cytokines and depressed mood, including excess negative affect and deficits in positive affect, will be entered in the regression models in their longitudinal format, thus reflecting all the measurements performed during the study (T_0 , $T_1 - T_{12}$). **Exploratory Aim** is tested using mixed-effects logistic regression, separately in the endotoxin and placebo groups, because the outcome (depressive episodes) is a binary variable repeatedly measured over 2 years. The predictor variables include the sum of POMS depression during 12 hours of experimental session, Cyberball Social Exclusion Task (T_2), Emotion Tasks (T_2), Social Choice Task (T_2), and Reward Tasks (Response, Learning, Motivation, Sensitivity) (T_2).

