Endotoxin elicits sickness symptoms (e.g., nausea, achiness) that will be assessed as potential covariates in statistical analyses. The battery of administered tasks could lead to excessive fatigue and non-compliance. This is not currently a concern in the parent study, but we will monitor participants' subjective response to the tasks, as well as current fatigue, and assess these variables either as potential covariates or as indicators that the experimental session requires modification. While we do not anticipate strong emotional response to any of the tasks, there is the potential for carryover effects without task counterbalancing. However, since the order is the same for the experimental and the control group, such effects should not impact the primary research questions assessing group differences.

REFERENCES

1. Blazer DG. Depression in late life: review and commentary. *J Gerontol A Biol Sci Med Sci*. 2003;58(3):249-265.
2. Depression Guideline Panel: Clinical Practice Guideline 5: Depression in Primary Care, vol 2: Treatment of Major Depression. In: US Department of Health and Human Services PHS, Agency for Health Care Policy and Research, ed. Rockville, MD.1993.
7. Kuehner C. Gender differences in unipolar depression: an update of epidemiological findings and possible explanations. *Acta Psychiatr Scand*. 2003;108(3):163-174.

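### A shared task order removes carry-over only if it is equal in every cell, so mood ratings soon after the 2 h exclusion task cannot be attributed to inflammation alone

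*Combined protocol and SAP*

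**What the plan says.** C.3 concedes that "there is the potential for carryover effects without task counterbalancing". It gives two reasons for not pursuing this: "we do not anticipate strong emotional response to any of the tasks", and "since the order is the same for the experimental and the control group, such effects should not impact the primary research questions".

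Other sections bear on the second reason:

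- **Timing (C.2.2).** "Behavioral tasks will be administered to coincide with peak onset of depressed mood", which the plan puts at 2 h. Cyberball is given at 2 h only and has no baseline value. C.2.6 also puts the social choice task and the recorded conversation with a trained listener in the session at 2 h.
- **Purpose of Cyberball (C.2.6).** It is listed under negative affect responding, with the rationale that inflammatory processes can "increase feelings of distress and related neural sensitivity".
- **Hypotheses (Specific Aims 1 and 2).** Negative affective responses to endotoxin are expected to be higher in females than in males, and in younger than in older females.
- **Analysis (C.2.8).** Cyberball at T2 is an Aim 1 outcome, and the key results are the effects of sex, condition and their interaction. Aim 2 repeats the design with age. "POMS Depression, DACL, Social Disconnection" are modelled at T0 and hourly from T1 to T12.

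No section says whether the T2 mood ratings come before or after the 2 h tasks, or plans an analysis limited to ratings made before them.

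**The concern.** A common order protects a comparison when the order effect is a constant: it is added to every cell and drops out of the difference. It does not protect a comparison when the reaction to the task depends on the factors being compared. Here the plan expects the reaction to exclusion to depend on condition and, through the aims and the outcome list, on sex and age.

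The mood outcomes that follow are close to what the task provokes, Social Disconnection most obviously. Ten of the twelve hourly post-injection ratings (T3-T12) come after the 2 h battery starts, and T2 may do so as well. A sex-by-condition or age-by-condition difference at T3 could therefore be partly a stronger reaction to being left out of the game, rather than stronger depressed mood produced by inflammation. The same ratings enter the Aim 3 cytokine-mood models and the 12-hour POMS sum in the Exploratory Aim.

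**Working it through.** The plan gives no figure for carry-over, so there is none to reproduce. The check has two parts.

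**1. The contrast.** Let a(g,c) be the carry-over in group g (F, M) and condition c (E, P). It adds to the sex-by-condition contrast

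[a(F,E) − a(F,P)] − [a(M,E) − a(M,P)].

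- Equal carry-over a in every cell gives (a − a) − (a − a) = 0. The C.3 reasoning holds in this case.
- Carry-over that differs by condition, but by the same amount in both sexes, also gives 0 for the interaction. It does not cancel from the endotoxin-placebo difference.
- If exclusion distress itself has a sex-by-condition interaction, which Aim 1 tests, and some of it persists, the term is not zero. Replacing sex by age gives the same result for Aim 2.

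**2. Size, by illustration.** The yardstick comes from C.2.9: d = 0.51 in older females and 0.003 in older males, so the implied interaction is 0.51 − 0.003 = 0.507 SD. Everything else is assumed, because the documents give no Cyberball interaction, decay rate or clock time.

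*Model A.* Exclusion at about 2.5 h adds an interaction of x SD that decays with half-life h hours. The term at hour t is x · 0.5^((t − 2.5)/h).

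| | x = 0.25, h = 1 | x = 0.5, h = 2 |
|---|---|---|
| T3 | 0.25 · 0.5^0.5 = 0.177 | 0.5 · 0.5^0.25 = 0.420 |
| T4 | 0.25 · 0.5^1.5 = 0.088 | 0.5 · 0.5^0.75 = 0.297 |
| T7 | 0.25 · 0.5^4.5 = 0.011 | 0.5 · 0.5^2.25 = 0.105 |
| T12 | 0.25 · 0.5^9.5 = 0.0003 | 0.5 · 0.5^4.75 = 0.019 |
| Mean T3-T12 | 0.035 | 0.139 |
| Mean T7-T12 | 0.004 | 0.052 |

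Divided by 0.507, this is 35-83% at T3, 7-27% for the T3-T12 mean and about 1-10% for T7-T12. C.2.2 says the earlier protocol ran 6 hours, so T7-T12 is the new extension.

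*Model B.* The Cyberball interaction equals the full 0.507 SD, a fraction λ reaches T3, and a fraction ρ persists each hour: 0.507 · λ · ρ^(t − 3).

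- λ = 0.1, ρ = 0.5: T3 = 0.051; T3-T12 mean = 0.010.
- λ = 0.25, ρ = 0.8: T3 = 0.127; mean = 0.057.
- λ = 0.5, ρ = 0.8: T3 = 0.254; mean = 0.113.
- λ = 0.5, ρ = 0.95: T3 = 0.254; mean = 0.203.

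The T3-T12 mean is thus 2-40% of 0.507. In both models the term falls with time, so T7-T12 is always the least exposed stretch. Whether it is also small depends on the decay. With λ = 0.5 its mean is 0.064 SD at ρ = 0.8 but 0.18 SD at ρ = 0.95. The latter implies a half-life of ln 0.5 / ln 0.95 = 13.5 h, longer than the session.

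**Scale against sampling error.** With 20 per cell, the standard error of a single-hour interaction is √(4/20) = 0.447 SD. For the T3-T12 mean, with an assumed within-person correlation of 0.6 and no baseline adjustment, it is 0.447 · √((1 + 9 · 0.6)/10) = 0.358 SD. If endotoxin had no direct group-by-condition effect on those ratings, the Model B terms would move a two-sided 5% test to between 5.0% and 8.8%.

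**The case against.** **The contrast is randomised.** Endotoxin against placebo within each group, and the difference between groups, remain valid as the total effect of endotoxin under this task schedule. The extra term also exists only if endotoxin changes exclusion distress differently by group, which is itself a differential affective response to endotoxin and within the aims as worded. This stands. A reader might infer that the plan would produce a false finding about affective sensitivity; the documents do not support that. The question is what the later mood ratings can be attributed to.

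**The sentence is modest.** C.3 says carry-over should not matter, not that it cannot, and it may have had effects of one task on the next in mind. It is also true that B.2 names prior depression history and inflammatory challenge for Cyberball, not sex or age, so that link rests on the Specific Aims and the outcome list. The remark in C.2.2 that "repeated exposure to behavioral tests of social exclusion might alter responses" concerns taking the test twice in a crossover and gives no evidence of persistence over hours. All of this softens the point, but the reasoning offered still covers only equal carry-over.

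**There is partial handling.** C.3 will monitor subjective response to the tasks as a potential covariate, and C.2.8 crosses the interaction with time. Neither settles it. Task reaction is measured after randomisation and is expected to be affected by endotoxin, so adjusting for it does not isolate the inflammation effect. The time interaction shows a pattern without saying which ratings carry which claim.

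**Direction is not known.** The reflective-listening conversation could relieve distress, and its order relative to Cyberball is not stated. The emotion regulation task in C.2.6 uses negative material but also trains up-regulation of positive emotion, and has no stated time. The net term could be smaller than illustrated, or of opposite sign.

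**Conclusion.** The C.3 inference does not hold under the plan's own hypotheses. Equal order gives equal carry-over only if reactions are equal, and the plan sets out to show that they are not. Post-task ratings, and their sex or age interaction, should be described as response to endotoxin plus the task battery. T1 precedes the 2 h battery; T2 cannot be classified from the documents.

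The size is unknown. Under the assumed values the term is greatest at T3-T4 (0.09-0.42 SD in Model A) and averages 0.01-0.20 SD over T3-T12 across both models. The upper end needs either an exclusion interaction about as large as the whole mood interaction the plan assumes, or very slow decay.

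Two stronger readings should be resisted. A reader might infer that the extension to 12 hours is most at risk because lingering distress would mimic delayed resolution. Under any steady decay it is least at risk, at 0.004-0.05 SD for half-lives of 1-2 h. A reader might also take the T3 percentages as the share of the Aim 1 effect that is artefact. They are the worst hour under assumed inputs, and the model uses all hours.

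**What to change.** 1. **C.3:** replace the sentence on common order with the limitation: carry-over cancels only if equal across cells, and ratings after the 2 h tasks reflect endotoxin plus the battery.
2. **C.2.6:** state the sequence of T2 mood ratings, observer ratings and tasks actually used in the parent study, and keep it identical for the younger women. C.2.3 reports 74 parent participants already complete, so a new rule cannot bind them, and a new order for the younger women alone would confound Aim 2.
3. **C.2.8, Aims 1 and 2:** keep the T0-T12 model. Add a pre-specified group-by-condition contrast on POMS Depression, DACL and Social Disconnection limited to ratings before the 2 h battery: T0-T2 if the T2 ratings precede the tasks, otherwise T0-T1. Pre-task here means before the 2 h battery, since C.2.4 also places affective tasks in the session before injection.

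The cost is wording and one extra contrast on data already collected. That contrast uses fewer ratings and is less precise, and if T2 was rated after the tasks it loses the 2 h peak. It should therefore stand beside the full model as an aid to attribution, not replace it.
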